4.2. Secondary Objectives

- 4.2.1. Study the safety, tolerability, and feasibility of Axitinib in patients with locally advanced biopsy-proven clear cell renal cell carcinoma prior to undergoing radical nephrectomy.
- 4.2.2. Assess disease-free survival and overall survival in patients with locally advanced biopsy proven clear cell renal cell carcinoma treated with 12 weeks of neoadjuvant Axitinib followed by radical nephrectomy.
- 4.2.3. Collect renal tissue, blood (serum, plasma, DNA, and PBMC), and urine for future correlative biomarker studies.

5. Assessment of Response

CT scans of the chest and abdomen will be evaluated by a urologist and an expert genitourinary radiologist. The urologist (investigator assessment) and the radiologist (independent assessment) will perform the tumor measurements. Response will be determined by the radiologist assessment. Tumor measurements will be documented in the tumor measurement form (one of the CRFs) and medical record. GURU will be used as electronic case report forms (CRF). RECIST version 1.0 criteria will be used as follows to quantify response to therapy:

- Complete Response (CR): Complete disappearance of renal mass.
- Partial Response (PR): At least a 30% decrease in the largest diameter (LD) of the renal mass taking as reference the baseline largest diameter.
- Progressive disease (PD): At least a 20% increase in the LD of the renal mass taking as reference the LD of the renal mass recorded since the treatment started. PD will also include development of any biopsy-proven metastatic disease.
- Stable Disease (SD): Neither sufficient shrinkage to qualify for PR nor sufficient increase to qualify for PD taking as reference the LD since the treatment started.
- Objective response rate (ORR) is defined as CR+PR.
- ORR will be evaluated when CT abdomen is done after 12 weeks of treatment (see Table 4).
- PD will be evaluated when CT abdomen is done after 7 weeks and 12 weeks of treatment (see Table 4).

6. Statistical Considerations

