To illustrate the use of these stopping rules, suppose 18 patients are treated in this study and evaluated for response and only 1 had ORR. We would close the study for lack of efficacy. If 2 patients out of the first 18 respond, then an additional 6 patients will be treated for a total of 24 patients. Likewise, if 6 out of 17 patients had PD, we would close the study for excessive PD.

The operating characteristics for the futility monitoring rule are shown in Table 1 and for the PD monitoring rule are shown in Table 2. The operating characteristics in Table 1 do not

account for early stopping due to excessive PD; likewise, the operating characteristics in Table 2 do not account for early stopping due to futility.

We plan to stop recruitment if we observe 2 treatment-related deaths. Treatment-related deaths are defined as deaths directly caused by study drug while the patients are taking the study drug, or intraoperatively, or within 30 days after nephrectomy, and the decision to classify the deaths as directly caused by study drug will be made by the study Principal Investigator. Perioperative mortality for patients undergoing radical nephrectomy is estimated to be between 1% and 4%¹³⁻¹⁵. The operating characteristics associated with this decision criterion are shown in Table 3. These probabilities were derived by running 1,000 simulations.

We also plan to stop recruitment if two or more patients a) cannot undergo radical nephrectomy as a result of participating in the study, or b) experience a delay in time to radical nephrectomy of more than 6 weeks from last axitinib dose, or c) experience inadequate healing post-operatively defined as fascial dehiscence requiring reoperation, or d) experience severe bleeding post-operatively defined as bleeding requiring reoperation.

Table 1. Operating Characteristics of the ORR Futility Monitoring Rule

Success Rate	Probability of Stopping Early	Sample Size		
		P ₂₅	P ₅₀	P ₇₅
0.05	0.775	18	18	18
0.10	0.455	18	24	24
0.15	0.221	24	24	24
0.20	0.106	24	24	24
0.25	0.039	24	24	24

Table 2. Operating Characteristics of the Excessive PD Monitoring Rule

Success Rate	Probability of Stopping Early	Sample Size		
		P ₂₅	P ₅₀	P ₇₅
0.10	0.056	24	24	24
0.15	0.165	24	24	24
0.20	0.346	12	24	24
0.25	0.537	8	19	24
0.30	0.724	6	11	24

Table 3. Operating Characteristics of the Treatment-Related Mortality Stopping Rule

$\pi_{\text{treatment-related mortality}}$	Probability of Stopping Early	Sample Size		
		P ₂₅	P ₅₀	P ₇₅

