6.2. Statistical Considerations for Secondary Objectives

- 6.2.1. To examine the safety of axitinib, we will tabulate reported adverse events (adverse events will be recorded per CTCAE v4.0).
- 6.2.2. To examine the tolerability of axitinib, we will use the FKSI-15 (Functional Assessment of Cancer Therapy-Kidney Specific Index-15, Appendix E) questionnaire and compare changes in response between different time points.
- 6.2.3. We will evaluate disease-free survival by plotting Kaplan-Meier curves and estimating median recurrence-free survival. Time to death or recurrence will be defined as the time from treatment start until death, recurrence or progressive disease, whichever comes first. Patients who did not die, recur or have progressive disease will be censored at date of last follow-up. These will be compared to contemporary, matched (2:1 matching, for age group, stage and grade), historical controls. Although small differences in recurrence-free and overall survival might not be detected in this current trial, this information will help us when designing future large trials with this particular agent.

7. Treatment Plan (Table 4)

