7.3. Post-treatment follow-up

- 7.3.1. Patients will be seen at week 19 (+/- 1 week) and evaluated with CT chest and abdomen (renal protocol), full laboratory analysis (CBC, CMP), collection of blood and urine for research, and full history and physical examination. Evidence of disease recurrence [If a patient develops any evidence of biopsy-proven RCC after axitinib/surgery (in the form of local disease or distant disease), the patient will be labeled as having disease recurrence] or treatment related morbidity will be recorded. Pathology will be reviewed and will be assessed for histology, Fuhrman grade, percentage tumor viability, pathologic tumor size, presence of venous, extracapsular, sinus, or nodal involvement.
- 7.3.2. A history, physical examination, medication list (Appendix J), ECOG Performance Status, Adverse Events, FKSI-15 questionnaire (Appendix E) will be performed and recorded in the medical record and appropriate CRFs on week 19.
- 7.3.3. Patients will be followed with similar evaluations every 4 months (+/- 2 weeks) for the first year, then every 6 months (+/- 2 weeks) for the next 2 years, , then yearly (+/- 1 month) until year 5 postoperatively. Evidence of recurrence or treatment related morbidity will be recorded.

8. Tissue, Blood, and Urine Banking

- 8.1. Tissue-Kidney biopsy specimen and kidney surgical specimen will be collected
 - 8.1.1. Kidney biopsy specimen. A total of 4 adequate biopsy cores are needed. Each core should undergo touch prep by cytopathologist to ensure biopsy quality (ie, malignant cell present with minimal necrosis/hemorrhage). More cores will be obtained if touch prep shows inadequate diagnosis (to obtain a total of 4 adequate cores).
 - 8.1.1.1. One core will be fixed for pathologic evaluation and sent for pathology department for review prior to starting treatment.
 - 8.1.1.2. Three cores will be immediately placed in 3 separate cryotubes, labeled appropriately, and stored at -70° to -80°C for future use.
 - 8.1.1.3. All 4 touch prep slides will be labeled appropriately, and stored at room temperature for future use.
 - 8.1.2. Kidney surgical specimen:
 - 8.1.2.1. Tissues from final kidney surgical specimen (4 pieces of tumor, 5-10mm diameter each; and 4 pieces of normal appearing kidney cortex, 5-10mm diameter each) will

be collected in the pathology department. Each piece will be placed in a separate cryotube, labeled appropriately, and stored at -70° to -80°C for future use.

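### The disease-free survival rule in 6.2.3 scores a living patient whose stable primary was never resected as event-free, and tumor left at surgery is covered only in part

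*Combined protocol and SAP*

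**What the plan says.** Section 6.2.3 defines the DFS time as "the time from treatment start until death, recurrence or progressive disease, whichever comes first". For everyone else it says: "Patients who did not die, recur or have progressive disease will be censored at date of last follow-up". The result is to be shown as Kaplan-Meier curves with a median, and compared with historical controls matched 2:1 on age group, stage and grade.

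The terms inside that definition are set elsewhere:

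- **PD (Section 5).** For the primary: "At least a 20% increase in the LD of the renal mass". For spread: "PD will also include development of any biopsy-proven metastatic disease".
- **Stable disease (Section 5).** "Stable Disease (SD): Neither sufficient shrinkage to qualify for PR nor sufficient increase to qualify for PD". It is therefore not a DFS event.
- **Recurrence (7.3.1).** A patient has recurred who "develops any evidence of biopsy-proven RCC after axitinib/surgery (in the form of local disease or distant disease").

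Patients who do not reach surgery appear in 6.1. Recruitment stops if two or more patients meet any of four criteria, the first being that they "cannot undergo radical nephrectomy as a result of participating in the study". Sections 7.2.6.2.4 and 7.2.12 call some patients treatment failures. None of these sections says how such patients enter DFS.

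**The concern.** DFS normally measures time free of disease after it has been removed. Here the clock starts while every patient has a renal tumor in place, and nothing in 6.2.3 requires the tumor ever to be removed. For a patient who is never resected, the endpoint behaves like progression-free survival: a tumor that stays in place without growing 20% counts as event-free time.

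Failure to reach surgery is one of the harms a neoadjuvant drug can cause, and under this rule it could appear as a good DFS result. Section 6.2.3 intends the survival data to inform the design of later, larger trials, so the definition matters even though DFS is secondary.

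**Working it through.** The documents state no DFS rate, median, event count or power, so there is no figure of the plan to reproduce. The check applies the rule to typical records and then sizes the gap.

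**Step 1. Apply the rule.** All patients below are alive and without PD.

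| Record | Recurrence under 7.3.1? | Scored in 6.2.3 |
|---|---|---|
| Stable at week 12, completely resected, no later disease | No | Censored, correctly |
| Stable or partial response, primary never removed | No (Step 2) | Censored as event-free |
| Macroscopic tumor left at surgery, biopsy-proven afterwards | It can be | Event, date not specified |
| Macroscopic tumor left at surgery, not biopsied | No | Censored as event-free |

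**Step 2. Could 7.3.1 cover an unresected primary?** It refers to disease after axitinib/surgery and does not explain the slash. If a primary still in place after axitinib alone counted, every patient with stable disease or a partial response would become a recurrence between the last dose and the nephrectomy that Table 4 places at week 13. That cannot be intended, so the second record has no route to an event other than PD or death.

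**Step 3. Size.** Inputs: N = 24 (6.1). Assumed, because the documents do not give them: k unresected patients, and DFS of S at the landmark in the other 24 − k.

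- Counted as events at about the planned surgery date: S(24 − k)/24.
- As written, followed event-free to the landmark: [S(24 − k) + k]/24. Excess = k/24.
- As written, lost and censored soon after planned surgery: about S. Excess = S·k/24.
- As written, with PD or death at five times the hazard of the others (assumed, exponential): [S(24 − k) + k·S⁵]/24. Excess = k·S⁵/24.

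The upper bound k/24 is 1/24 = 4.2 points, 2/24 = 8.3 points and 3/24 = 12.5 points for k = 1, 2 and 3.

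Example with k = 2 and an assumed 5-year DFS of 70% in the others, so that 3-year S = 0.7^0.6 = 0.807:

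| Handling of the two patients | 3 years | Excess | 5 years | Excess |
|---|---|---|---|---|
| Counted as events | 22 × 0.807/24 = 74.0% | – | 22 × 0.70/24 = 64.2% | – |
| As written, event-free throughout | 82.3% | 8.3 | 72.5% | 8.3 |
| As written, censored early | 80.7% | 6.7 | 70.0% | 5.8 |
| As written, fivefold hazard | 76.9% | 2.9 | 65.6% | 1.4 |

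A Kaplan-Meier simulation (24 patients, 60 months, 4,000 runs) gave 73.9%, 82.2%, 80.7% and 76.7% at 3 years, and 63.9%, 72.2%, 69.8% and 65.3% at 5 years, in the same row order. This agrees with the formulas to within about 0.3 points.

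The median can move too. With an assumed 5-year DFS of 50% in the others and k = 2, the 5-year value is (22 × 0.5 + 2)/24 = 54.2% as written, if both are followed event-free, and 11/24 = 45.8% with them as events. On the expected curve the median then lies after five years in one case and before it in the other.

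**Step 4. Chance that such a patient occurs.** For an assumed non-resection rate p, P(at least one of 24) = 1 − (1 − p)^24:

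| p | At least one | At least two |
|---|---|---|
| 1% | 21% | 2% |
| 2% | 38% | 8% |
| 5% | 71% | 34% |
| 10% | 92% | 71% |

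**The case against.** The strongest reply is that the case may never arise. Entry is limited to patients suitable for curative nephrectomy (3.2.3), a surgical date is fixed before treatment (7.2.2), and surgery remains the planned path after permanent discontinuation or week-7 progression (7.2.6.2.4, 7.2.12). A patient who is unresectable because of progression already has an event. This stands: with no such patient the effect is zero.

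A reader might infer from the stopping criterion in 6.1 that the plan expects patients to miss surgery. It does not say so. The criterion is a safety trigger, and it concerns inability caused by the study, not refusal.

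A reader might also infer that any tumor left behind at surgery is scored as disease-free. Section 7.3.1 does not support that, because biopsy-proven local disease after surgery can be labeled a recurrence. What stays open is residual disease that is not biopsied, and the event date.

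Later PD and death still count, so the excess can shrink with follow-up. This also stands, with two limits. Early loss helps less than it seems: 6.7 of 8.3 points remain at 3 years in the example. And continued tumor assessment until progression is spelled out only for patients removed for toxicity (such as 7.2.6.2.5), while 7.3.3 times its visits from surgery and names recurrence and morbidity.

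Finally, a bias toward axitinib against the controls is tempting to assert. Matching on grade makes nephrectomy in the controls likely, but the documents do not state it.

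**Conclusion.** The point holds as a defect in the endpoint definition. Under 6.2.3 as written, a living patient with a stable, never-resected primary is event-free until PD, death or last follow-up. Residual tumor at surgery is covered only where 7.3.1 applies.

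The overstatement at a landmark after planned surgery is at most k/24: 4.2 points for one such patient and 8.3 for two. That bound requires the patients to be followed to the landmark without PD or death. The documents do not support saying that DFS will be overstated, or that each such patient adds a fixed 4.2 points at every landmark. The number of such patients, their later course and the DFS of the others are all assumptions here.

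DFS is secondary, with no stated power or decision rule. The objective response analysis and the stopping rules are unaffected. Severity is minor.

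**What to change.** In 6.2.3:

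- Count as a DFS event a patient who cannot undergo nephrectomy, dated at the planned week-13 surgery date, unless PD or death came first.
- Count as a DFS event macroscopic disease left unresected at the end of surgery, dated at surgery. Exclude nodal disease that was fully resected. The protocol requires node dissection (7.2.13) and treats nodes up to 2 cm as N0 (3.2.1), so occult nodes will be found that controls may not have been assessed for equally.
- Keep all treated patients in the denominator. Objective 4.2.2 describes axitinib followed by nephrectomy and could be read as dropping the unresected. That would report S instead of S(24 − k)/24: 70.0% instead of 64.2% at 5 years in the example.
- Cite the 7.3.1 definition of recurrence.
- Apply the same residual-disease rule to the matched controls where it is recorded.
- Report patients who decline surgery without progression separately, with a sensitivity analysis counting them as events.

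The cost is a short paragraph in 6.2.3 and probably two data items: completeness of resection, and the reason for no nephrectomy. The lists in 7.2.13 and 7.3.1 name neither. Reported DFS may be slightly lower, and control data on residual disease may be incomplete.

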7.1. Pre-treatment screening

- 7.1.1. Patients will undergo routine staging evaluation to include CT chest and abdomen with renal protocol, to evaluate extent of local disease and rule out the presence of metastatic disease. If the patient had these CT scans done at an outside facility within 4 weeks of enrollment in the trial, then these CT scans may not need to be repeated at MD Anderson, as long as the actual CD or DVD of the films are available (and not just the report) and as long as the protocols used for the CT scans were similar to those at MD Anderson (i.e. renal protocol with intravenous contrast needs to be used). If the CD or DVD is from an outside facility, it has to be reviewed by our urologist and/or radiologist here to check the quality of the images (for example, if the CT scan was done within 4 weeks of screening, but was done without intravenous contrast, the investigators might decide to repeat the CT scan prior to starting study treatment). If only a report is available, the CT scans will need to be repeated at MD Anderson to be eligible for the study. Bone scan and CNS imaging will be done at the discretion of the attending physician for patients with indications to do so (elevated alkaline phosphatase, bone pain for bone scan, and CNS symptoms for CNS imaging). An EKG will be done.
- 7.1.2. CBC, CMP (sodium, potassium, chloride, carbon dioxide, calcium, glucose, BUN, creatinine, magnesium, phosphorus, lactate dehydrogenase, AST, ALT, alkaline phosphatase, total and direct bilirubin, albumin, total protein), PT, PTT, TSH, free T3, free T4, and urinalysis will be obtained within 4 weeks of study enrollment. A pregnancy test will be done for women of childbearing potential within 4 weeks of enrollment and again on the day of starting therapy as explained in Section 3.2.
- 7.1.3. A history, physical examination, medication list (Appendix J), ECOG Performance Status, Adverse Events, and EKG will be performed and recorded in the medical record within 4 weeks of study enrollment as noted in Table 4.
- 7.1.4. Patients that meet eligibility criteria will undergo image-guided biopsy (18G core needle biopsy x 4 cores and touch prep-1 core for pathologic diagnosis, 3 optional cores for tissue banking) of their primary tumor to establish the presence of clear cell histology.
- 7.1.5. If a prospective patient has untreated hypertension at presentation, the patient will be placed on a medical regimen to control the hypertension, prior to enrollment (Enrollment

means when the patient meets all the study eligibility criteria and is ready to be registered in CORe step 2).

7.2. Treatment Phase

7.2.1. Eligible patients will provide written informed consent.

7.2.2. Prior to the initiation of therapy, a surgical date will be established.

7.2.3. Treatment Assignment: Each patient will receive a total of 12 weeks of axitinib. Patients will take the last dose of axitinib 1.5 days prior to surgery.

7.2.4. Adverse events monitoring and reporting:

7.2.4.1. Adverse events:

7.2.4.1.1. The investigator is responsible for determining the attribution of adverse events to study drug.

7.2.4.1.2. Adverse events will be documented in the medical record and entered into the case report form according to the Recommended Adverse Event Recording Guidelines for Phase II protocol (see table below).

Recommended Adverse Event Recording Guidelines					
Attribution	Grade 1	Grade 2	Grade 3	Grade 4	Grade 5
Unrelated	Phase I	Phase I	Phase I Phase II	Phase I Phase II Phase III	Phase I Phase II Phase III
Unlikely	Phase I	Phase I	Phase I Phase II	Phase I Phase II Phase III	Phase I Phase II Phase III
Possible	Phase I Phase II	Phase I Phase II Phase III	Phase I Phase II Phase III	Phase I Phase II Phase III	Phase I Phase II Phase III
Probable	Phase I Phase II	Phase I Phase II Phase III	Phase I Phase II Phase III	Phase I Phase II Phase III	Phase I Phase II Phase III
Definitive	Phase I Phase II	Phase I Phase II Phase III	Phase I Phase II Phase III	Phase I Phase II Phase III	Phase I Phase II Phase III

7.2.4.1.3. Adverse events will be assessed at each patient visit, documented in the medical record, and entered into the CRFs. Adverse events should be treated appropriately. Such treatment may include changes in axitinib treatment including possible interruption or discontinuation, starting or stopping concomitant treatments, changes in the frequency or nature of assessments, hospitalization, or any other medically required intervention. Once an adverse event is detected, it should be followed until its resolution, and assessment should be made at

each visit of any changes in severity, the suspected relationship to the axitinib, the interventions required to treat it, and the outcome. In addition, Pfizer requires reporting of serious adverse events on the M.D. Anderson SAE forms. Reporting of adverse events will be done according to NCI Common Terminology Criteria for Adverse Events (CTCAE) version 4.0. The following items will be recorded at least:

- Event description
- Date of onset of AE
- CTCAE grade/severity (1,2,3,4,5)
- Relationship to treatment with axitinib (unrelated, unlikely, possible, probable, highly probable/definite)
- Action taken (none, temporarily discontinued agent, drug treatment given/specify, permanently discontinued agent, non-drug treatment given/specify, hospitalization)
- Date of AE stop
- Outcome (recovered without sequelae, recovered with sequelae, ongoing, worsened, death)
- Serious AE (yes, no)

7.2.4.2. Serious Adverse events (SAE):

7.2.4.2.1. SAE reporting-SAEs will be recorded on a SAE form (Appendices G and H), in addition to the CRF AE documents. SAEs will be reported within 24 hours to Pfizer (Please see Pfizer SAE reporting guidelines in the appendix section)

7.2.4.2.2. SERIOUS ADVERSE EVENT REPORTING – M. D. Anderson Cancer Center: The following SAE Reporting Requirements, since this is an MDACC sponsored IND study, and all SAEs must be reported to IND Sponsor representative – the IND Office - according to the following:

7.2.4.2.2.1. A serious adverse event is – any adverse drug experience occurring at any dose that results in any of the following outcomes:

- Death
- A life-threatening adverse drug experience – any adverse experience that places the patient, in the view of the initial reporter, at immediate risk of death from the adverse experience as it occurred. It does not include an adverse

experience that, had it occurred in a more severe form, might have caused death

- Inpatient hospitalization or prolongation of existing hospitalization
- A persistent or significant disability/incapacity – a substantial disruption of a person’s ability to conduct normal life functions
- A congenital anomaly/birth defect

7.2.4.2.2.2. In this protocol, we will not report those hospitalizations resulting from routine treatment not associated with any deterioration in condition, treatment for a pre-existing condition that is unrelated to axitinib and has not worsened since the start of axitinib; or for treatment on an emergency outpatient basis for an event not fulfilling any of the definitions of a SAE given above and not resulting in hospital admission.

7.2.4.2.2.3. Important medical events that may not result in death, be life-threatening, or require hospitalization may be considered a serious adverse drug experience when, based upon appropriate medical judgment, they may jeopardize the patient or subject and may require medical or surgical intervention to prevent one of the outcomes listed in this definition. Examples of such medical events include allergic bronchospasm requiring intensive treatment in an emergency room or at home, blood dyscrasias or convulsions that do not result in inpatient hospitalization, or the development of drug dependency or drug abuse (21 CFR 312.32):

- Important medical events as defined above, may also be considered serious adverse events. Any important medical event can and should be reported as an SAE if deemed appropriate by the Principal Investigator or the IND Office .
- All events occurring during the conduct of a protocol and meeting the definition of a SAE must be reported to the IRB in accordance with the timeframes and procedures outlined in

“University of Texas M. D. Anderson Cancer Center Institutional Review Board Policy on Reporting Serious Adverse Events”. Unless stated otherwise in the protocol, all SAEs, expected or unexpected, must be reported to the IND office, regardless of attribution (within 5 working days of knowledge of the event).

- All life-threatening or fatal events, expected or unexpected, and regardless of attribution to the study drug, must have a written report submitted within 24 hours (next working day) of knowledge of the event to the IND office
- The MDACC “Internal SAE Report Form for Prompt Reporting” will be used for reporting to the IND office.
- Serious adverse events will be captured from the time the patient signs consent until 30 days after the last dose of drug. Serious adverse events must be followed until clinical recovery is complete and laboratory tests have returned to baseline, progression of the event has stabilized, or there has been acceptable resolution of the event.
- Additionally, any serious adverse events that occur after the 30 day time period that are related to the study treatment must be reported to the IND office. This may include the development of a secondary malignancy.

7.2.4.2.2.4. Reporting to FDA:

- Serious adverse events will be forwarded to FDA by the IND Office, according to 21 CFR 312.32.

7.2.4.2.2.5. It is the responsibility of the PI and the research team to ensure serious adverse events are reported according to the Code of Federal Regulations, Good Clinical Practices, the protocol guidelines, the sponsor’s guidelines, and Institutional Review Board policy.

7.2.5. Axitinib Starting Dose: Patients will receive up to 12 weeks of axitinib orally. Axitinib is started at a dose of 5mg BID (twice each day) taken orally with food. Dose adjustments, including dose increase or dose reduction should be based on adverse events experienced

by the individual patient. Axitinib should be taken beginning on day 1 of the study. Doses should be taken approximately 12 hours apart. Patients should be instructed to take their doses at approximately the same times each day. Patients should be instructed that if they vomit anytime after taking a dose, that they must not “make it up” with an extra dose, but instead resume subsequent doses as prescribed. Any missed dose may be taken late up to 3 hours before the next scheduled dose, otherwise, it should be skipped. If doses are missed or vomited, this must be indicated in the source documents and CRFs. A pill diary (Appendix J) will be provided where the patient will record the date, time (AM or PM), and dose of axitinib taken, as well as the blood pressure measurement prior to axitinib intake (Appendix J). Available axitinib dose levels are listed below.

Dose Level	Dose	Dispensed As
+2	10 mg BID	2 X 5 mg Tablets BID
+1	7 mg BID	1 X 5 mg Tablet BID + 2 X 1mg Tablets BID
0 (Starting Dose)	5 mg BID	1 X 5 mg Tablet BID
-1	3 mg BID	3 X 1mg Tablets BID
-2	2 mg BID	2 X 1mg Tablets BID

7.2.6. Axitinib dose modifications during trial: Patients will receive axitinib at a starting dose of 5 mg orally twice daily until disease progression, unmanageable toxicity, withdrawal of consent occurs, or until 1.5 days prior to surgery.

7.2.6.1. Axitinib dose increase: Because previous studies indicated variable drug levels in patients, the axitinib dose will be increased in a step-wise fashion from 5 mg twice daily to 7 mg twice daily, then to 10 mg twice daily, in the absence of axitinib-related toxicity greater than or equal to grade 2 for a continuous 2-week period and in the absence of hypertension (defined as two blood pressure [BP] measurements of > 150/90 mmHg taken in the clinic > 1 hour apart) at any point during study. The clinical judgment of the treating physician should be exercised in up-titrating the axitinib dose.

7.2.6.2. Axitinib dose modifications for adverse events (other than hypertension and proteinuria):

7.2.6.2.1. Patients developing axitinib-related CTCAE Grade 1 adverse events may have their dose increased to next dose level.

- 7.2.6.2.2. Patients developing axitinib-related CTCAE Grade 2 adverse events should have their dose continued at the same dose level.
- 7.2.6.2.3. Patients developing axitinib-related CTCAE Grade ≥ 3 adverse events should have their dose reduced as indicated in section 7.2.6.2.6
- 7.2.6.2.4. If patients need to have their axitinib treatment interrupted for 2 or more continued-week period due to unmanageable toxicities or any other reason, their axitinib treatment will be permanently discontinued and considered treatment failures. Patients will then proceed to surgery to have their kidney tumors removed.
- 7.2.6.2.5. Patients removed from treatment for intolerable toxicity should still be followed with regular tumor assessments (every 4 months for 1 year, every 6 months for the next 2 years and every 12 months for one more year) until disease progression or start of new treatment, and for survival thereafter until study completion.
- 7.2.6.2.6. The criteria for dose modification for study-drug-related adverse events are summarized in the table below:

CRITERIA FOR DOSE MODIFICATION FOR AXITINIB-RELATED ADVERSE EVENTS OTHER THAN HYPERTENSION OR PROTEINURIA	
Related Adverse Events	INTERVENTION
Grade 1	Increase to next dose level, or maintain if already at the maximum dose
Grade 2	Continue at same dose level
Grade 3 nonhematologic treatment-related toxicity* or Grade 3 hematologic toxicity	Decrease dose to one lower dose level
Grade 4 hematologic treatment-related toxicity**	Interrupt dosing; re-start at one lower dose level as soon as improvement to CTCAE Grade ≤ 2 occurs within 2 weeks. If a patient requires dose reduction below 2 mg BID when above fails, consideration should be given to stop axitinib if this recurs.
Grade 4 nonhematologic treatment-related toxicity	Stop Axitinib

* Patients who develop Grade 3 nonhematologic toxicities that are controlled with symptomatic medications or Grade 3 asymptomatic biochemistry laboratory abnormalities may be continued at the same dose level at the discretion of the investigator.

** Patients who develop Grade 4 lymphopenia or Grade 4 asymptomatic biochemistry laboratory abnormality may continue study treatment without interruption.

- 7.2.6.3. Axitinib dose-reduction for hypertension:
- 7.2.6.3.1. Electronic BP monitors will be provided to each patient for home use. Instructions to use them will be provided (Appendix F) and demonstration of their use will be done in the visit

prior to starting axitinib intake. Patients will self-monitor BP at home twice daily (before each axitinib dose). All BP measurements will be recorded in a diary (Appendix J) and brought to the clinic at each clinic visit. Patients will be instructed to inform their physicians in the event of systolic BP greater than 150 mmHg or diastolic BP greater than 100 mmHg, or if they develop symptoms related to elevated BP (e.g. headache or visual disturbance). During normal business hours the patient will call the urology research nurse for instructions. Outside of normal business hours, the patient will call the urologist on call through the page operator, and inform the urologist that they are enrolled in the axitinib trial. The urologist on call will then contact one of the axitinib study members ([name], [name], [name] or [name]) for further instructions. Written contact information will be provided to each patient prior to initiation of axitinib (Appendix I)

- 7.2.6.3.2. New or additional antihypertensive therapy should be started if 2 BP readings, preferably taken in the clinic and separated by at least 1 hour, show the following: 2 systolic BP readings greater than 150 or 2 diastolic BP readings greater than 100 mm Hg. Alternately, the dose of existing antihypertensive medication(s) may be increased. If the patient is already on maximal antihypertensive treatment, the axitinib dose should be reduced by 1 dose level.
- 7.2.6.3.3. Patients who have 2 systolic BP readings, separated by at least 1 hour, greater than 160 mm Hg, or 2 diastolic BP readings, separated by at least 1 hour, greater than 105 mm Hg, should have treatment with axitinib held. (Note: if axitinib is held, patients receiving antihypertensive medications should monitor closely for hypotension and restart axitinib at one lower dose level as soon as BP is <150/100 mm Hg. Plasma half-life of axitinib is 2 – 6 hours and BP usually decreases within 1-2 days following dose interruption.) Treatment with axitinib should be restarted at 1 lower dose level as soon as the systolic blood pressure reduces to less than 150 mm Hg and the diastolic BP reduces to less than 100 mm Hg.
- 7.2.6.3.4. Patients who develop recurrent systolic hypertension (2 BP readings separated by at least 1 hour show systolic pressure >150 mm Hg) or recurrent diastolic BP >100 mm Hg following previous axitinib dose reduction should undergo another dose reduction by one dose level.
- 7.2.6.3.5. Patients removed from treatment for intolerable toxicity should still be followed with regular tumor assessments (every 4 months for 1 year, every 6 months for the next 2 years and every 12 months for one more year) until disease progression or start of new treatment, and for survival thereafter until study completion. Guidance on dose interruption and reduction for hypertension is summarized in the table below.

7.2.6.3.6. The antihypertensive medications (if the patient is taking any) will be tapered after axitinib is stopped, in order to maintain a blood pressure level that is less or equal to 140/90. Once the patient is at this blood pressure level, his blood pressure/blood pressure medications will be managed by his primary care physician.

HYPERTENSION MANAGEMENT PLAN FOR AXITINIB			
Degree of Blood Pressure Elevation			Management
Systolic Pressure	OR	Diastolic Pressure	
2 BP readings separated by at least 1 hour show systolic pressure >150 mm Hg		2 BP readings separated by at least 1 hour show diastolic pressure >100 mm Hg	If not on maximal antihypertensive treatment, institute new or additional antihypertensive medication and maintain dose of axitinib. If on maximal antihypertensive treatment, reduce axitinib to one lower dose level.
2 BP readings separated by at least 1 hour show systolic pressure >160 mm Hg	OR	2 BP readings separated by at least 1 hour show diastolic pressure >105 mm Hg	Interrupt dosing*; adjust antihypertensive medication; as soon as BP is less than 150/100 mm Hg, restart axitinib at one lower dose level.
Recurrent hypertension following previous dose reduction (2 BP readings separated by at least 1 hour show systolic pressure >150 mm Hg)	OR	Recurrent diastolic BP >100 mm Hg (2 BP readings separated by at least 1 hour) following previous dose reduction	Repeat axitinib dose reduction by one lower dose level. If a patient requires dose reduction below 2 mg BID, interrupt dosing adjust antihypertensive medication; as soon as BP is less than 150/100 mm Hg, restart axitinib. Consideration should be given to stop axitinib if this recurs.

* If axitinib is held, patients receiving antihypertensive medications should monitor closely for hypotension. Plasma half-life of axitinib is 2 – 6 hours and BP usually decreases within 1-2 days following dose interruption.

7.2.6.4. Axitinib dose-reduction for proteinuria:

7.2.6.4.1. If urinalysis shows protein qualitative level \geq 100 (equivalent to \geq 2+ proteinuria on dipstick), perform 24-hour urine collection. Dosing may continue while waiting for test results. [Equivalence of protein qualitative levels on urine dipstick and urinalysis are as follows: 1+ on dipstick is equivalent to 30 on urinalysis, 2+ on dipstick is equivalent to 100 on urinalysis, 3+ on dipstick is equivalent to 300 on urinalysis, and 4+ on dipstick is equivalent to >2000 on urinalysis]

7.2.6.4.2. If < 2 g proteinuria/24 hour is reported, continue dosing at the same dose level.

7.2.6.4.3. If ≥ 2 g proteinuria/24 hours is reported, hold dosing and repeat 24 hour urine collection for proteinuria and creatinine clearance (interval at investigator discretion) until proteinuria is < 2 g/24 hours. Restart axitinib at the same dose or one lower dose level at discretion of the investigator.

7.2.6.4.4. Patients removed from treatment for intolerable toxicity should still be followed with regular tumor assessments (every 4 months for 1 year, every 6 months for the next 2 years and every 12 months for one more year) until disease progression or start of new treatment, and for survival thereafter until study completion.

